7.2 General Study Procedures

A signed and dated IRB-approved informed consent must be obtained before any study-specific procedures are performed. Procedures that are part of routine care are not considered study-specific procedures and may be used at screening to determine eligibility. All subjects will be screened for eligibility before randomization. Only eligible subjects will be randomized into the study.

During treatment, assessments and procedures can be performed within 3 days of the planned visit. It is recommended that dosing occur on the same day of the week (eg, if first dose is administered on Monday, all subsequent doses should be administered on a Monday), however a ± 3 -day dosing and study procedure window is allowed.

The following laboratory analytes in [Table 4](#) will be assessed at various times throughout the study:

Table 4. Laboratory Analytes

Chemistry	Coagulation	Hematology	Other Labs
Sodium	PT or INR	RBC	LDH
Potassium	PTT or aPTT	Hemoglobin	Pregnancy
Chloride		Hematocrit	qPCR for talimogene laherparepvec DNA
Calcium		Platelets	
Magnesium		WBC	
Phosphorus		Differential*	HSV-1 antibody
Uric acid		• Neutrophils	BRAF ^{V600}
Total protein		• Eosinophils	Biomarkers
Albumin		• Basophils	• Blood
BUN		• Lymphocytes	• Archived tumor tissue
Creatinine		• Monocytes	• Fresh tumor biopsy tissue
Total bilirubin			
Alkaline-phosphatase			
AST			
ALT			
Glucose			

* 3-part differential if 5-part unable to be performed

All tests (except for real-time polymerase chain reaction [qPCR], HSV-1 antibody and biomarkers) are to be performed at the local laboratory and test results are to be fully and routinely recorded on the CRFs. Serine/threonine protein kinase B-Raf V600 (BRAF^{V600}) mutation analysis may be performed at a central laboratory. Missed tests that are not done must be reported as such on the CRFs. The qPCR, HSV-1 antibody

and biomarker tests will be performed at a central laboratory and results will not be recorded on the CRFs.

7.2.1 Screening and Randomization

The following procedures are to be completed during the screening period at time points designated in the Schedule of Assessments ([Table 2](#) and [Table 3](#)):

- Confirmation that the Informed Consent Form has been signed
- Demographic data including sex, age or date of birth, race, and ethnicity will be collected in order to study their possible association with subject safety and treatment effectiveness.
- Medical and surgical history: The Investigator or designee will collect complete medical and surgical history. Medical history will include information on the subject's concurrent medical conditions. Record all findings on the medical history CRF.
- Vital signs (systolic/diastolic blood pressure, heart rate, respiratory rate, temperature): Subject must be in a supine position in a rested and calm state for at least 5 minutes before blood pressure assessments are conducted. If the subject is unable to be in the supine position, the subject should be in most recumbent position as possible. The position selected for a subject should be the same that is used throughout the study and documented on the vital sign CRF. Record all measurements on the vital signs CRF.
- Physical examination as per standard of care
- Documentation of concomitant medications
- ECOG performance status assessment
- Local Laboratory Assessments
 - within ≤ 28 days prior to randomization
 - hematology panel: hemoglobin, hematocrit, white blood cell (WBC) count with 5-part differential (3-part differential if 5-part unable to be performed), red blood cell (RBC) count, platelets
 - chemistry panel: sodium, potassium, chloride, calcium, magnesium, phosphorous, uric acid, total protein, albumin, blood urea nitrogen (BUN), creatinine, total bilirubin, alkaline phosphatase, AST, ALT, glucose
 - LDH
 - coagulation: PT or INR and PTT or aPTT
 - within ≤ 3 days prior to randomization
 - serum or urine pregnancy test for female subjects of childbearing potential
- Clinical tumor assessments, including clinical measurement of cutaneous, subcutaneous, and palpable nodal tumor lesions by caliper to be used as baseline assessment
- Radiographic tumor imaging (including CT scan, positron emission tomography [PET]/CT scan, magnetic resonance imaging [MRI] or ultrasound) of the chest, abdomen, pelvis, and all other sites of disease, MRI of the brain (required to be completed for all subjects), to be used as baseline imaging

- Recording of serious adverse events that occur after subject signs informed consent. Serious adverse events will be reported to Amgen within 24 hours following the investigator's knowledge of the event
- Review of inclusion and exclusion criteria
- Randomization in IVR system

Subjects who are determined not eligible after screening must be screen-failed in the IVR system and the reason for the screen failure provided. Subjects who do not meet all eligibility criteria may be rescreened once at the discretion of the investigator. If a subject is being rescreened, he or she may need to re consent to the study to ensure that the IRB/IEC-approved main consent form is signed within 28 days of randomization. Subjects who are determined not eligible after rescreen must be screen-failed in the IVR system and the reason for the screen-failure provided. Subjects may only be randomized once into this study.

7.2.2 Treatment

Treatment begins when the first dose of protocol-required therapies is administered to a subject (Arm 1) or the subject undergoes surgery (Arm 2).

The following procedures will be completed during the treatment period at the times designated in the Schedule of Assessments ([Table 2](#) and [Table 3](#)).

- Vital signs (systolic/diastolic blood pressure, heart rate, respiratory rate, temperature): Subject must be in a supine position in a rested and calm state for at least 5 minutes before blood pressure assessments are conducted. If the subject is unable to be in the supine position, the subject should be in most recumbent position possible. The position selected for a subject should be the same that is used throughout the study and be documented on the vital signs CRF.
 - Arm 1: prior to talimogene laherparepvec administration on day 1 of weeks 1, 4, 8, 12, and prior to surgery
 - Arm 2: within 3 days prior to surgery
- Physical examination as per standard of care
 - Arm 1: within 3 days prior to talimogene laherparepvec administration on day 1 of week 1 and within 3 days prior to surgery, and prior to talimogene laherparepvec administration on day 1 of weeks 4 and 8
- ECOG performance status
 - Arm 1: prior to talimogene laherparepvec administration on day 1 of weeks 4 and 8 and within 3 days prior to the surgery

- Local laboratory assessments
 - Arm 1: prior to talimogene laherparepvec administration on day 1 of weeks 1, 6, 12. Screening laboratory values may be used for week 1 day 1 assessment if completed within 3 days of study treatment initiation. On treatment tests can be performed within 3 days of the planned visit. Results should be reviewed prior to the administration of study drug
 - Hematology panel: hemoglobin, hematocrit, WBC with 5-part differential (3-part differential if 5-part unable to be performed), RBC, platelet
 - Chemistry panel: sodium, potassium, chloride, calcium, magnesium, phosphorus, uric acid, total protein, albumin, BUN, creatinine, total bilirubin, alkaline phosphatase, AST, ALT, glucose
- Central laboratory assessments:
 - Blood for HSV-1 antibody serostatus
 - Arm 1: within 3 days of day 1 of week 1 (prior to administration of talimogene laherparepvec)
 - Blood for biomarker analysis
 - Arm 1: within 3 days of day 1 of week 1 (prior to administration of talimogene laherparepvec) and week 6 (prior to administration of talimogene laherparepvec) and within 3 days prior to the day of surgery
 - Arm 2: within 3 days prior to the surgery
 - Tumor biopsy for biomarker analysis
 - Arm 1: within 3 days of day 1 of week 1 (prior to talimogene laherparepvec administration) and at the time of surgery. At the time of surgery the tumor biopsy should be marked as injected lesion or non-injected lesion.
 - Arm 2: at the time of surgery
 - Swab of cold sore, vesicles and other lesions suspected to be herpetic in origin (if any) for qPCR testing of talimogene laherparepvec DNA:
 - Arm 1 - Subject should return to the clinic within 3 days of the occurrence of a reportable lesion suspected to be herpetic in origin. The lesion should be evaluated by the investigator and swabbed if HSV infection is suspected. A qPCR analysis will be performed on the swab sample to evaluate whether the talimogene laherparepvec DNA is detectable in the sample.
 - Archived formalin-fixed paraffin-embedded tumor tissue (block or unstained tumor slide) from either the primary tumor or a metastatic lesion, and the associated pathology reports, must be submitted to the central laboratory within 28 days after randomization for biomarker analyses

- BRAF^{V600} mutation testing/status may be obtained in a number of ways as listed below:
 - previously known BRAF^{V600} tumor status: BRAF^{V600} tumor status result, obtained from a local laboratory prior to screening for this study will be acceptable and should be available within 28 days after randomization
 - previously unknown BRAF^{V600} tumor status: Archived formalin-fixed paraffin-embedded tumor tissue (block or unstained tumor slide) from either the primary tumor or a metastatic lesion (as described above) will be analyzed at a local laboratory or submitted to the central laboratory within 28 days after randomization for BRAF^{V600} tumor status determination
- Radiographic tumor imaging assessments
 - Arm 1: day 1 of week 12 (\pm 2 weeks) or within 2 weeks prior to surgery if a subject ends talimogene laherparepvec prior to week 12
 - Radiographic imaging must include CT scan, PET/CT, MRI, or ultrasound of the chest, abdomen, and pelvis and all other sites of disease. In addition, CT scan or MRI of the brain will only be performed if symptoms or signs suggestive of CNS metastasis are present. The imaging modality selected (eg, CT or MRI) should remain constant for any individual subject.
- Clinical tumor assessments (clinical measurement of cutaneous, subcutaneous, or palpable nodal tumor measurement by caliper)
 - Arm 1: day 1 of week 12 (\pm 2 weeks) or within 1 week prior to surgery if a subject ends talimogene laherparepvec prior to week 12
- Response assessment per modified WHO response criteria ([Appendix D](#))
 - Arm 1: day 1 of week 12 (\pm 2 weeks) or within 2 weeks prior to surgery if a subject ends talimogene laherparepvec prior to week 12
- Histological tumor assessment of the surgical specimens. Surgical specimens will be assessed for presence of viable tumor and tumor margin status for cutaneous and subcutaneous tumor.
 - Tumor-free margins (negative margins, R0) resection is defined by pathologist as absence of ink on the tumor. All other resections of viable tumor are described as tumor positive margins resections, and are defined as
 - R1 resection - complete resection with no grossly visible tumor left behind as defined by the surgeon, or
 - R2 resection - partial resection with grossly visible tumor left behind as defined by the surgeon.
 - A pathological complete response (pCR) in Arm 1 is defined as no evidence of viable tumor cells on complete pathological evaluation of the surgical specimen per institutional standards of care
- Recording of adverse events at each visit
- Recording of serious adverse events at each visit. Serious adverse events will be reported to Amgen within 24 hours following the investigator's knowledge of the event

- Documentation of concomitant medications at each visit
- Arm 1 - Reporting pregnancy in a female subject or a female partner of a male subject while the subject is taking talimogene laherparepvec treatment and through 3 months after end of treatment ([Section 9.3](#))
- Arm 1 - Reporting lactation case in a female subject while the subject is taking talimogene laherparepvec treatment and through 3 months after end of treatment ([Section 9.3](#))
- Talimogene laherparepvec administration
 - Arm 1: day 1 of weeks 1, 4, 6, 8, 10, and 12 or until all injectable tumors have disappeared, intolerance of study treatment, whichever occurs first. Subjects who experience growth in existing tumors or the appearance of new tumors will be allowed to remain on talimogene laherparepvec treatment until week 12 of therapy unless, in the opinion of the investigator and in consultation with the sponsor's medical monitor, immediate surgical resection or any other treatment for melanoma is warranted.
- Surgery
 - Arm 1: For subjects who complete 12 weeks of talimogene laherparepvec treatment, surgical resection of melanoma lesion(s) will be performed at any time during weeks 13 to 18. Subjects who stop talimogene laherparepvec prior to week 12 due to disappearance of all injectable tumor lesions, intolerance to talimogene laherparepvec, or any other reason will undergo surgical resection of melanoma lesion(s) or tissue where melanoma was present before CR within 1 to 6 weeks after the last dose of talimogene laherparepvec. Refer to [Appendix F](#) for surgery guidelines.
 - Arm 2: Surgical resection of melanoma tumor lesion(s) will be performed after randomization any time during weeks 1 to 6. Refer to [Appendix F](#) for surgery guidelines.

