Median (range) time to response among the 78 subjects in the talimogene laherparepvec arm with a response was 4.1 (1.2 to 16.7) months, whereas among the 8 in the GM-CSF arm with a response, it was 3.7 (1.9 to 9.1) months. Fifty-four percent of talimogene laherparepvec objective responders and 48% of talimogene laherparepvec durable responders exhibited “interval progression”, which is transient locoregional or distant progression including appearance of new lesions, before ultimately achieving response (Kaufman et al, 2013). When investigator-reported response rates (decrease in lesion area: PR, 50 to <100%; CR, 100%) of 3,916 measurable lesions (average 13) in 285 subjects treated by talimogene laherparepvec in the OPTiM Study were analyzed retrospectively, CR and PR rates in injected lesions were 47% and 17%, respectively. CR and PR in non-injected non-visceral lesions were 22% and 12%, respectively. CR and PR in visceral lesions, which were also non-injected, were 9% and 6%, respectively (Andtbacka et al, 2014).

The most common side effects in the OPTiM study were chills (talimogene laherparepvec, 49%; GM-CSF, 9%), pyrexia (43%; 9%), injection-site pain (28%; 6%), nausea (36%; 20%), influenza-like illness (30%; 15%), and fatigue (50%; 36%). Grade \geq 3 adverse events occurred in 36% of subjects receiving talimogene laherparepvec and 21% of subjects receiving GM-CSF. The only grade 3/4 adverse events occurring in \geq 5 of subjects was cellulitis (talimogene laherparepvec, n=6 [2.1%]; GM-CSF, n=1 [$<$ 1%]). Of 10 fatal adverse events in the talimogene laherparepvec arm, 8 were attributable to disease progression. The remaining 2 fatal adverse events

(sepsis in the setting of salmonella infection; myocardial infarction) were not considered treatment-related per investigator.

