#### **4.1.2 Secondary Endpoint**

##### **4.1.2.1 Efficacy Endpoints**

##### **4.1.2.1.1 Tumor Response (Arm 1 Only)**

The overall tumor response is evaluated up to the earlier of surgical resection or subsequent anti-cancer therapy. Lesion-level response is evaluated up to the earliest event of start of subsequent anti-cancer therapy, merge with another lesion, or resection. Subject-level response is evaluated up to the earliest event of start of subsequent anti-cancer therapy or a partial or complete lesion resection.

Following endpoints will be analyzed for tumor response analysis,

- The overall tumor response is per the modified WHO criteria of tumor.
- Tumor response in injected/uninjected lesion(s)
  - The subject-level injected and uninjected responses will be based on the tumor burden of only injected index lesions including injected new measurable lesions, or the tumor burden of only uninjected index lesions including uninjected new measurable lesions, respectively.
  - The lesion-level injected and uninjected response will evaluate the change of the area of each individual lesion.
- Similar to tumor response in injected/uninjected lesions, lesion-level and subject-level response may also be conducted for lesion subtypes, eg, cutaneous / subcutaneous, nodal.

For the subject-level tumor response by tumor burden type (injected, uninjected lesions), a response is achieved if the percentage of the specific tumor burden type reduction from baseline for both baseline and new measurable lesions (if applicable) is at least 50%. Overall tumor burden is calculated at a visit as the sum of tumor areas of all lesions of the same type. The incidence of subject-level tumor response will be reported as the proportion of subjects with an evaluable tumor burden of the corresponding type that achieves a response.

The incidence of lesion-level response will be reported as the proportion of evaluable lesions in response. A lesion is in response if the decrease in tumor area is  $\geq 50\%$ .

All overall tumor burden and lesion response analyses will be based on bi-dimensional lesion measurements reported at a tumor assessment and will not consider injected lesion longest diameters reported at the time of investigational product administration forms.

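### For Arm 1 subjects who complete dosing, the only scheduled pre-surgery response assessment is not tied to the last dose or to surgery: it can precede the sixth dose and be up to 62 days before resection

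*Protocol*

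**What the plan says.** Protocol 7.2.2 gives two timing rules for Arm 1. Subjects who reach week 12 have imaging, caliper measurement and response assessment at day 1 of week 12 ± 2 weeks. Subjects who stop earlier have imaging and response assessment tied to the operation: "or within 2 weeks prior to surgery if a subject ends talimogene laherparepvec prior to week 12". Their caliper measurement is due within 1 week before surgery.

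Dosing in the same section is "Arm 1: day 1 of weeks 1, 4, 6, 8, 10, and 12 or until all injectable tumors have disappeared". For subjects who complete dosing, "surgical resection of melanoma lesion(s) will be performed at any time during weeks 13 to 18".

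Table 2 marks imaging and response assessment at screening, week 12 and long-term follow-up; the week 13 to 18 column is empty in those rows.

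SAP 4.1.2.1.1 sets the cut-off: "The overall tumor response is evaluated up to the earlier of surgical resection or subsequent anti-cancer therapy". Protocol 10.1.1.2 likewise stops at resection. The same SAP section excludes the lesion diameters recorded on the dosing forms, so those cannot serve as a later reading.

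**The concern.** Response to the neoadjuvant course, overall and in injected and uninjected lesions, is a secondary objective. For a subject who completes dosing it rests on one scheduled visit, fixed to a calendar week with a wide window and to neither event that gives the reading its meaning: the end of dosing and the resection. A reading early in the window describes a shorter course than the subject received and leaves a long stretch before surgery unmeasured. A reading after resection leaves the subject with no usable post-baseline assessment.

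The SAP does not say how such a subject is counted. Table 2 of the SAP puts the tumor response analysis on the ITT set, where the subject would probably count as a non-responder. The subject-level rates for injected and uninjected lesions use only subjects with an evaluable tumor burden, so there the subject would drop out. SAP 9.3.1 refers missing efficacy data back to the endpoint definitions, which do not cover this case.

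**Working it through.** The plan states no precision or timing figure for tumor response, so there is none to reproduce. The check is calendar arithmetic.

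**Inputs.** Dosing, assessment and surgery weeks are from Protocol 7.2.2. The ± 3-day dosing window is from Protocol 3.1 and 7.2. Arm 1 has about 75 subjects (150 randomized 1:1, Protocol 10.2). Exact 80% intervals are from SAP Table 2.

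**Study days.** Day 1 of week w = 1 + 7(w − 1).
- Dose 5 (week 10): day 64; with ± 3 days, days 61 to 67.
- Dose 6 (week 12): day 78; with ± 3 days, days 75 to 81.
- Assessment window: 78 ± 14 = days 64 to 92, which is 29 days.
- Surgery: day 1 of week 13 = day 85, to the end of week 18 = day 126, which is 42 days.

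**Before dose 6.** Days 64 to 77 precede nominal day 78: 14 of 29 days (48%). The nominal visit is itself the day of dose 6.

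**Before dose 5.** This is possible on day 64 before that day's injection, or on days 64 to 66 if dose 5 is up to 3 days late. If instead the interval windows of Protocol 6.2.1.1 accumulate (+5 days once, then +3 each time), dose 5 can be as late as 1 + 26 + 3 × 17 = day 78, and dose 6 as late as day 95, after the assessment window has closed.

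**Gap to surgery.**
- Longest: 126 − 64 = 62 days.
- From the nominal day: 85 − 78 = 7 to 126 − 78 = 48 days.
- Latest assessment with earliest surgery: 85 − 92 = −7, that is, 7 days after resection.
- Early stoppers, for imaging and response: 0 to 14 days.

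**How common, for illustration only.** Assume each day in each window is equally likely; the documents give no distribution.
- After resection: surgery on days 85 to 91 with a later assessment gives 7 + 6 + 5 + 4 + 3 + 2 + 1 = 28 pairs. 28/(29 × 42) = 28/1218 = 2.3% overall, and 28/(29 × 7) = 28/203 = 14% if surgery is in week 13.
- Before dose 5, with dose 5 on days 61 to 67: 6/(29 × 7) = 6/203 = 3.0%, or 10/203 = 4.9% counting the same day.
- More than 14 days before surgery: 965/1218 = 79%.

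**Does the general window cure it?** Protocol 7.2 says "During treatment, assessments and procedures can be performed within 3 days of the planned visit". If that overrode the specific ± 2 weeks, the window would be days 75 to 81. It could still precede dose 6, and be 126 − 75 = 51 days before surgery. The two windows are not reconciled.

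**Scale.** One reclassified subject moves the rate by 1/75 = 1.3 percentage points. The exact 80% interval at n = 75 has a half-width of 5.2 points at 8/75 (11%) and 7.8 points at 30/75 (40%); this range of rates is assumed.

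**The case against.** The strongest defence is that a nominal end-of-dosing visit is a recognisable choice. The objective speaks of response during treatment, and a fixed time from first dose makes subjects comparable on that scale. Anchoring to surgery gives that up: assessments now span 92 − 64 = 28 days, and under a post-dose, pre-surgery rule they would nominally span 126 − 78 = 48 days. Early stoppers also need a surgery anchor, because week 12 may fall after their resection. This stands as a genuine trade-off. It does not justify a window in which nearly half the days precede the last dose.

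It is also fair that missing both final doses and assessing after resection are edge cases, and that only descriptive Arm 1 clinical response is touched.

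Some stronger inferences are tempting, and the documents do not support them:
- **That the response rate is mis-measured, and downward.** It can be. Late responses may be missed, but so may late progression, and nothing gives the net direction or size.
- **That post-resection readings contaminate the rate.** Both documents stop evaluation at resection, so the effect is a missing assessment.
- **That the window closes before the typical response.** Protocol 2.2 reports "Median (range) time to response among the 78 subjects in the talimogene laherparepvec arm with a response was 4.1 (1.2 to 16.7) months". Those subjects had unresectable disease and were generally treated at least until week 24. Resection curtails observation by design, so this figure does not measure bias here.
- **That sites would favour the early end for surgical planning.** No passage says so, and wanting a current scan points equally to the late end.
- **That early stoppers' response can be dated before its own data.** The 1-week and 2-week limits can both be met. Appendix D derives response from the measurements, so this is an editorial mismatch.

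**Conclusion.** The point holds in limited form. For Arm 1 subjects who complete dosing, the single scheduled pre-surgery response assessment can comply with the protocol and still precede the sixth dose, or be up to 62 days before resection. At the extremes it can precede the fifth dose or come up to 7 days after resection and be lost to the endpoint. The clinical response rates can therefore be mis-measured.

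The day counts rest only on the stated windows and nominal weeks; the percentages for gaps and edge cases rest on the equal-likelihood assumption. R0 and pCR come from the surgical specimen and RFS does not use this visit, so none of them is affected. The change should be made because it protects a secondary endpoint at very little cost; it does not bear on the primary conclusion.

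**What to change.** In Protocol 7.2.2 and the Table 2 footnotes, require that imaging, clinical measurement and response assessment for every Arm 1 subject take place after the last injection given and before resection. Preferably, place them within the 2 weeks before surgery already used for early stoppers, with one common limit for all three. The first requirement alone cuts the longest gap from 62 to 48 days at nominal dosing; the 2-week limit cuts it to 14. It is workable even in the tightest case under the ± 3-day dosing window: dose 6 on day 81 and surgery on day 85 leave days 82 to 84.

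In SAP 4.1.2.1.1, name that assessment as the response time point, and state that subjects with no valid pre-resection assessment count as non-responders in the ITT response rate. If some visits have already taken place, which the documents do not establish, the SAP can still define this handling and tabulate assessment timing relative to last dose and surgery.

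The cost is wording and a visit-window edit. The number of scans, the dosing and the surgery timing do not change. The small downside is that time from first dose to assessment will vary more with the surgery date.
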